5.1. Primary Objective

The primary objective of this study is to compare the efficacy of HORIZANT Extended-Release Tablets 600 mg BID compared with matched placebo on the primary alcohol consumption outcome endpoint, PSNHDD during the last 4 weeks of the maintenance phase, among subjects with AUD. PSNHDD will also be analyzed during other time periods (i.e., the last 8, 12, 16, 20, and 24 weeks of the maintenance period) in exploratory analyses.

5.2. Secondary Objective

Secondary objectives are separated into two categories: key secondary objectives and supportive secondary objectives. The key secondary objective is to compare HORIZANT to placebo on the percentage of subjects abstinent from alcohol during the last 4 weeks of treatment. The supportive secondary study objectives are to assess other treatment benefits, including: reduction in other alcohol consumption endpoints, alcohol-related craving and consequences, mood, smoking, sleep quality, safety, and tolerability.

6. Investigational Plan

This study is a double-blind, randomized, placebo-controlled, parallel group, multi-site study designed to assess the efficacy of HORIZANT Extended-Release Tablets compared with placebo to reduce drinking in 346 subjects (173 in each group) who report 4 or more Diagnostic and Statistical Manual of Mental Disorders − Fifth Edition (DSM-5[™]) symptoms of AUD and who meet the drinking criteria outlined hereafter. This study will be conducted at 10 clinical sites. If eligible for the study, subjects will be randomized using a stratified permuted block randomization procedure with "clinical site" as the stratification variable in an approximate 1:1 ratio (targeting 173 subjects per group) to receive either HORIZANT Extended-Release Tablets or placebo for 26 weeks (1 week escalation; 24 weeks maintenance; 1 week taper).

Subjects will be seen in the clinic at screening, at randomization and 11 other times during the study. During the Week 1 dose escalation period (midway through the week) and during the maintenance period (Weeks 2 to 25), subjects will be contacted once per week by telephone at non-clinic visit weeks to encourage study drug compliance and to assess withdrawal, AEs, and concomitant medications. A final follow-up telephone interview will occur during Weeks 28 to 29 (1 to 2 weeks after the end of dosing).

An overview of the study design is provided in Figure 2. Study assessments and procedures will be performed at the visits and time points outlined in the Schedule of Assessments (Table 5).

[figure not shown]

Figure 2: Overview of Study Design

HORIZANT for Alcohol Use Disorder
Protocol Number: NCIG-006

NCIG, NIAAA, NIH

Table 5: Schedule of Assessments

	Sere	een	Ti- trate		Maintenance										Taper		Safety Follow- up							
Clinic Visit #	0	1		2		3		4		5		6		7		8		9		10		11	12	
Study Week	-2 to -1	Day -1	1	2	Mid week 2 & 3	4	5	6	7	8	9	10	11	12	13 - 15	16	17- 19	20	21- 23	24	25	26	EOS ^a /27	28- 29
Informed Consent	X																							
Alcohol Breathalyzer	X	X		X		X		X		X		X		X		X		X		X		X	X	
Urine Drug Screen ^b	X	X		X		X		X		X		X		X		X		X		X		X	X	
Locator Form	X																							
Demographics	X																							
Medical History	X	X																						
Physical Exam	X	X																					X	
MINI V 7.0	X																					\mathbf{x}^{c}		
Clinical Chemistry ^d	X					X				X				X		X		X		X		X	X	
Vital Signs ^e	X	X				X				X				X		X		X		X		X	X	
ECG	X																						X	
Prior and Concomitant Meds	X	X	X	X	X	X	X	X	X	X	X	X	X	X	X	X	X	X	X	X	X	X	X	X
CIWA-AR	X	X	X	X	X	X	X	X	X	X	X	X	X	X	X	X	X	X	X	X	X	X	X	
Eligibility Checklist	X	X																						
Blood for DNA Genomics Testing f		X																						
Blood for RNA Expression Testing		X																		X				
Blood for PK/Medication Compliance ^g														X				X		X				
Blood spot for PEth		X																				X		
Drug compliance/ accountability				X		X		X		X		X		X		X		X		X		X	X	
Pregnancy Test + birth control	X	X				X				X				X		X		X		X			X	

	Scre	een	Ti- trate		Maintenance										Taper		Safety Follow- up							
Clinic Visit #	0	1		2		3		4		5		6		7		8		9		10		11	12	
Study Week	-2 to -1	Day -1	1	2	Mid week 2 & 3	4	5	6	7	8	9	10	11	12	13 - 15	16	17- 19	20	21- 23	24	25	26	EOS ^a /27	28- 29
Weight	X	,														Х							X	
Drinking Goal		X																						
AEs	\mathbf{x}^{h}		X	X	X	X	X	X	X	X	X	X	X	X	X	X	X	X	X	X	X	X	X	X
C-SSRS		X		X		X		X		X		X		X	14	X	18	X	22	X		X	X	
RANDOMIZATION		X																						
Brief Telephone Interview ⁱ			X		X		X		X		X		X		X		X		X		X			
Take Control		X		X		X		X		X		X		X		X		X		X		X		
Exit Interview																							X	
Treatment Referral																							X	
Follow-Up Telephone Interview			7																					X
Final Subject Disposition																								X
Subject Reported Outcomes																								
Family History of Alcohol Problems		X																						
BIS		X																						
ImBIBe		X				X				X				X		X		X		X		X		
TLFB	X	X		X		X		X		X		X		X		X		X		X		X	X	
Drinking question ^j				X		X		X		X		X		X		X		X		X		X	X	
ACQ-SR-R		X		X		X		X		X		X		X		X		X		X		X		
Fagerström Test for Nicotine Dependence		X																						
Smoking quantity/frequency		X		X		X		X		X		X		X		X		X		X		X	X	
PSQI		X				X				X				X		X		X		X		X		
BAI		X				X				X				X		X		X		X		X		

HORIZANT for Alcohol Use Disorder Protocol Number: NCIG-006

	Scre	een	Ti- trate									Mair	itenan	ce								Taper		Safety Follow- up
Clinic Visit #	0	1		2		3		4		5		6		7		8		9		10		11	12	
Study Week	-2 to -1	Day -1	1	2	Mid week 2 & 3	4	5	6	7	8	9	10	11	12	13 - 15	16	17- 19	20	21- 23	24	25	26	EOS ^a /27	28- 29
BDI-II		X				X				X				X		X		X		X		X		
POMS		X				X				X				X		X		X		X		X		
Other Services Used for Alcohol Use Problems		X				X				X				X		X		X		X			X	

^a EOS=end of study. These assessments are to be done at Week 27 or if the subject discontinues early and agrees to a final clinic visit.

^b Test for opioids, cocaine, amphetamines, methamphetamine, tetrahydrocannabinol (THC), buprenorphine, methadone or benzodiazepines.

^c Only the AUD module is performed at Week 26.

^d AST, ALT, total bilirubin, creatinine, GGT.

^e Sitting blood pressure and heart rate.

f Only for subjects who consent to provide this sample.

^g For each subject, blood collections should be scheduled at different times relative to the morning dose at these 3 clinic visits.

^h Only SAEs will be reported from the time of signing informed consent until the first dose of investigational product administration. Thereafter, AEs and SAEs will be reported for the duration of the study.

ⁱ AEs, concomitant medications, CIWA-AR, and drug compliance reminder.

Only asked to subjects who are no longer participating in clinic visits and not willing to providing TLFB drinking data.

7. Study Interventions

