Primary: The primary outcome measure examines the hypothesis that HORIZANT Extended-Release Tablets will increase the PSNHDD compared to placebo during the last 4 weeks of the maintenance period (Study Weeks 22-25). A "heavy drinking day" is 4 or more drinks per drinking day for women and 5 or more drinks per drinking day for men. Drinking data will be collected by the Timeline Followback (TLFB) method. If during the last 4 weeks of the maintenance period of the study, the subject does not come back for clinic visits or provide TLFB data but agrees to telephone contact, then the subject will be asked if there were any heavy drinking days during the final study period. These data will be used to determine the primary efficacy endpoint when TLFB data are missing, otherwise the data will be imputed as having a heavy drinking day during this period.

Secondary: Secondary efficacy endpoints will also be analyzed over the last 4 weeks of treatment.

- 1. Percentage of subjects abstinent from alcohol (key secondary endpoint)
- 2. Percentage of subjects with a World Health Organization (WHO) drinking risk category decrease of:
 - a. at least 1-level
 - b. at least 2-levels
- 3. Percentage of days abstinent per week
- 4. Percentage of heavy drinking days per week
- 5. Weekly mean number of drinks per week
- 6. Weekly mean drinks per drinking day
- 7. Cigarettes smoked per week among smokers
- 8. Alcohol craving score [Alcohol Craving Scale Short Form (ACO-SR-R)]
- 9. Alcohol related consequences (ImBIBe) score
- 10. Pittsburg Sleep Quality Index (PSQI) score
- 11. Beck Anxiety Inventory (BAI) score
- 12. Beck Depression Inventory Scale II (BDI-II) score

Safety Endpoints Safety endpoints will be evaluated over the entire treatment and follow-up periods.

- 1. Vital signs
- 2. Blood chemistries
- 3. Urine drug screen results
- 4. Blood alcohol concentration (BAC) by breathalyzer
- 5. AEs
- 6. Electrocardiogram (ECG) results

- 7. Clinical Institute of Withdrawal Alcohol Revised (CIWA-AR) scores
- 8. Profile of Moods States (POMS) scores
- 9. Frequency of subjects with suicidal ideation at any time during the treatment period –Columbia-Suicide Severity Rating Scale (C-SSRS)

Compliance: Self report of compliance with investigational products and gabapentin plasma levels.

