8.9. Maintenance Phase

During Study Weeks 2 through 25 of the maintenance phase of the study, subjects will be seen in person at the clinical site 9 times and assessed by telephone 16 times. Week 26 is dose taper and there is a final clinic visit at Week 27 at the end of dose taper.

An alcohol breathalyzer will be administered at each visit, prior to any study assessments, to determine if the subject meets the BAC requirement of a BAC \leq 0.020 before proceeding with assessments. A urine drug test will be performed at each visit. At each of the clinic visits, subjects will meet with one or more study staff members who will systematically assess AEs since the last visit, take vital signs, administer questionnaires (CIWA-AR and C-SSRS), inquire about other medication use and assess drinking by TLFB. Clinical chemistry, pregnancy test for women of child-bearing potential and birth control methods (if female), blood for study drug compliance, and subject's weights will be collected in accordance with the schedule in Table 5. In addition, subjects will complete the battery of questionnaires in accordance with the schedule in Table 5.

Brief telephone assessments will occur weekly between in-clinic visits. The final in-clinic assessment will occur during Week 27. This visit should be scheduled after the subject takes the last dose of study drug.

Subjects will view a single module of Take Control that is expected to have a run-time of 10-15 minutes during each clinic visit. After completion of the Take Control module, a new supply of investigational product will be given and the bottle(s) from the previous period will be collected and a tablet count will be performed for accountability. Bottles with unused tablets will be returned to the subject. The dosing schedule will be reviewed and the subject will be provided instructions on how to complete the drug card to track tablet consumption. The subject will be instructed to bring the bottle(s) and drug cards with them to the next visit so the site staff can perform drug accountability (tablet counts). The subject will also be instructed to contact site staff if they are experiencing any intolerable AEs and are contemplating drug discontinuation.

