8.11. Final Clinic Visit

The final clinic visit occurs during Week 27; at which time the subject has completed taking investigational product. In addition to the assessments previously stated, subjects will have an Exit Interview assessment. The subject will be asked about their drinking for his/her impression of whether he/she was receiving active drug or placebo, if they felt that the medication helped drinking, how they would describe their experience taking the medication, if they would recommend it to a friend, if they would take it again if they needed further treatment in the future, and a question about desire to please people. The subject will be provided with a referral to a treatment program for their alcohol dependence. If a subject withdraws from the study early for any reason, the subject should be asked to return to the clinic for the conduct of all of the final clinic visit assessments.

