8.13. Duration of Subject Participation

The total time period that each individual subject will participate is 31 weeks including up to 2 weeks for screening, 26 weeks of study interventions, and final safety and efficacy follow-up the week after completing treatment (Week 27), and a final safety follow-up telephone contact from 1-to-2 weeks after completion of study drug dosing.

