9.2. Safety Endpoints

Safety endpoints will be analyzed over the entire treatment and follow-up period.

- 1. Vital signs
- 2. Blood chemistries
- 3. BAC by breathalyzer

- 4. Urine drug tests
- 5. AEs
- 6. ECG results
- 7. CIWA-AR scores
- 8. POMS scores
- 9. Frequency of subjects with suicidal ideation at any time during the treatment period (C-SSRS)

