11.21. MINI

The MINI (paper version 7.0) is a short structured diagnostic interview, developed jointly by psychiatrists and clinicians in the United States and Europe, for DSM-5 and ICD-10 psychiatric disorders (Sheehan et al-1998). With an administration time of approximately 15 minutes, it was designed to meet the need for a short but accurate structured psychiatric interview for multicenter clinical trials and epidemiology studies and to be used as a first step in outcome tracking in non-research clinical settings. Diagnoses recorded on the MINI will be recorded on the interview form and entered into an eCRF. The individual items of the Alcohol Use Disorders Module will be also collected on an eCRF in addition to all other diagnoses. At the last study visit, the Alcohol Use Disorders Module will be assessed again, but the initial drinking question will not be asked and the time period for which the questions apply has been revised to "the past month" instead of the past 12 months.

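### POMS is a safety endpoint for treatment and follow-up, but Table 5 leaves it out of the end-of-study column, so none is scheduled after the last dose in completers or at exit in early leavers

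*Protocol*

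**What the plan says.** Section 9.2 of the protocol lists nine safety endpoints, with POMS scores as item 8, under the statement "Safety endpoints will be analyzed over the entire treatment and follow-up period". The synopsis says the same: "Safety endpoints will be evaluated over the entire treatment and follow-up periods".

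Table 5 (Section 6) marks POMS at Day -1 and at Weeks 4, 8, 12, 16, 20, 24 and 26. The EOS/27 and Weeks 28-29 cells are blank.

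Section 8.9 separates these two visits: "Week 26 is dose taper and there is a final clinic visit at Week 27 at the end of dose taper". Of the Week 27 visit it adds: "This visit should be scheduled after the subject takes the last dose of study drug". Section 8.13 describes Week 27 as the final safety and efficacy follow-up.

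For early exit, Table 5 footnote a states: "These assessments are to be done at Week 27 or if the subject discontinues early and agrees to a final clinic visit". Section 8.11 says that after an early withdrawal "the subject should be asked to return to the clinic for the conduct of all of the final clinic visit assessments". Section 8.15 names a pregnancy test (females), weight, vital signs, ECG, clinical chemistry, C-SSRS, TLFB and adverse events, and then refers to Table 5 for whatever else belongs to the end-of-study visit.

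**The concern.** The endpoint list promises POMS over follow-up as well as treatment, yet the schedule stops it before dosing ends. The end-of-study column does two jobs, so a single blank cell removes two measurements: the post-dosing score in subjects who finish, and the exit score in subjects who leave.

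This matters somewhat more than a routine blank. Sections 4.3.6 and 4.3.11 state that the drug class raises the risk of suicidal thoughts or behavior, and POMS is the mood scale that the protocol classes as a safety measure. BDI-II and BAI are efficacy endpoints and are also unmarked at EOS/27, so no mood scale is scheduled off drug or at exit. A POMS summary by arm would then cover scheduled on-study visits only, although Section 9.2 describes a wider window.

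**Working it through.** No power or error-rate figure is involved. The check is a comparison of sections, plus two small counts.

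**1. EOS/27 cell for each Section 9.2 safety endpoint (Table 5)**

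| Safety endpoint | EOS/27 | Weeks 28-29 |
|---|---|---|
| Vital signs | marked | blank |
| Blood chemistries | marked | blank |
| Breathalyzer BAC | marked | blank |
| Urine drug tests | marked | blank |
| Adverse events | marked | marked |
| ECG | marked | blank |
| CIWA-AR | marked | blank |
| POMS | **blank** | blank |
| C-SSRS | marked | blank |

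POMS is the only one of nine without a mark at EOS/27. Table extraction does not explain this. The POMS row has all 24 week cells, with its last mark at Week 26. The next row, Other Services, also has 24 cells, skips Week 26 and is marked at EOS/27.

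**2. Does other text fill the gap?** Section 8.9 ties the questionnaires to Table 5. Section 11.26 describes POMS without giving a timing. Section 8.15 does not name it, and its remaining assessments are those of the end-of-study visit, which excludes POMS. The Weeks 28-29 call (Section 8.12) covers adverse events and medications. Nothing fills it.

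**3. Where the Week 26 visit falls in dosing**
- Anticipated use by Visit 11, from Table 6: 12 + 5×28 + 3×56 + 28 = 348 tablets.
- Scheduled use to the end of Week 25, from Table 7: Week 1 is 3×1 + 4×2 = 11; Weeks 2-25 are 24×14 = 336; the total is 347.
- Difference: 348 − 347 = 1 tablet.

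The two tables agree on the overall total: 347 + 7 taper tablets = 354, as Table 6 states. The Week 26 visit is nominally on the first taper day, one tablet in. Section 8.7 allows a 3-day window, so the actual visit may fall some days into the taper. Either way the subject is still dosing.

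**4. Early leavers.** Section 12.5 assumes 15% dropout per arm: 0.15 × 346 = 51.9, or about 52 subjects.

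**5. Age of the last score at exit.** POMS visits are 4 weeks apart from Week 4 to Week 24. A subject leaving in that range has a last score up to about 4 weeks old. A subject leaving before Week 4 has only the Day -1 score.

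**The case against.** The strongest reply is that little is lost.

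- **Suicidality and mood events are still captured.** C-SSRS is marked at EOS/27 and named in Section 8.15. Adverse events are collected at withdrawal, at EOS and at Weeks 28-29, and reasons for discontinuation are recorded. A reader might infer that mood worsening which causes exit, or follows stopping, cannot appear in the comparison between arms. The protocol does not support that: what is missing is a POMS score, not the safety signal as a whole.
- **Some off-drug scores will exist.** Section 8.14.1.2 keeps subjects who stop drug in the study with all assessments, so later POMS visits can be off drug. The gap concerns those who complete dosing and those who leave the study.
- **The Section 9.2 sentence is a general lead-in.** Only adverse events are marked at Weeks 28-29, and ECG is done only at screening and EOS, so the sentence cannot promise every measure at every follow-up point. The blank at Weeks 28-29 is therefore no fault. The argument is weaker at EOS/27, where POMS alone is missing. Item 9 of the same list is expressly limited to the treatment period, whereas POMS carries no such limit.
- **Week 26 is a taper visit.** A reader might say that the last POMS reflects mood at full dose. With one taper tablet already taken, a 3-day window and no recall period stated in Section 11.26, that cannot be said of every subject.

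The MINI alcohol module might also look like the same gap, because Section 11.21 says "At the last study visit, the Alcohol Use Disorders Module will be assessed again" while Table 5 places it at Week 26. It is not the same. Section 12.4.8 treats the module as an exploratory Week 26 measure covering the last 4 weeks of maintenance. The efficacy questionnaires likewise target that window, so their blank EOS cells contradict nothing.

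These replies narrow the consequence. They do not reconcile Section 9.2 with Table 5.

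**Conclusion.** The mismatch is real and minor. As scheduled, POMS cannot be analyzed over follow-up in subjects who complete dosing, because none is planned after the last dose. Early leavers have none planned at exit.

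The figure of about 52 subjects is an upper bound. It rests on the sample-size assumption of 15% dropout. Some leavers will decline a final visit, and others will leave at or near a scheduled POMS. The protocol gives no figure for how far leavers' mood differs from that of stayers, so no size of bias can be stated.

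The primary and key secondary endpoints are unaffected. Section 12.4.4 describes no POMS analysis; that may sit in the statistical analysis plan and is not part of this point.

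**What to change.** Mark POMS in the EOS/27 column of Table 5, which through footnote a also schedules it at early exit, and add it to the list in Section 8.15. The cost is an amendment to one table cell and one sentence, plus one more self-completed electronic questionnaire of 65 adjectives at a visit that already takes place. No change to the MINI module or the efficacy questionnaires is needed.

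If the sponsor does not want the extra scores, the alternative is to state in Section 9.2 and the synopsis that POMS is evaluated through Week 26 only. That makes the text consistent but leaves POMS without a post-dosing or exit score.

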7.1. Investigational Products: HORIZANT Extended-Release Tablets and Placebo

HORIZANT Extended-Release Tablets, 600 mg, are white to off-white, oval-shaped tablets debossed with "GS LFG". HORIZANT Extended-Release Tablets may contain occasional black/grey spots.

Placebo tablets debossed with "GS LFG" that are identical in appearance to HORIZANT Extended-Release Tablets will also be used in this study.

Both the HORIZANT Extended-Release Tablets and placebo tablets will be provided by XenoPort Inc., Santa Clara, CA.

7.2. Investigational Product Packaging, Labeling, and Distribution of Drug Kits to Sites

Investigational products will be provided in drug kits containing 14 bottles of either HORIZANT Extended-Release Tablets or placebo in each kit. Each bottle contains 30 tablets and each kit contains a total of 420 tablets. Each subject is scheduled to receive a total of 354 tablets, thus providing a sufficient supply of tablets for the entire study for a single subject in one kit. Kits will be shipped periodically to sites during the study depending on enrollment.

The study number and a brief protocol title that does not link the subject with an alcohol research study will be preprinted on each bottle label. The label will also have a kit number, the number of tablets contained in the bottle, storage conditions, and the words "Caution: New Drug – Limited by Federal law to investigational use" and "Keep Out of Reach of Children". A separate label will be supplied to affix to the bottle each time a bottle is dispensed. This label will contain the clinical site name, clinical site phone number and 24/7 emergency phone number, and places to record the subject number and the date dispensed.

7.3. Investigational Product Storage

Kits should be stored at room temperature (within the range of 59°F to 86°F) in a secured area at the clinical site.

7.4. Investigational Product Dispensing

The dispensing plan is provided in Table 6. At each visit when bottles are dispensed the appropriate number of drug diary cards will be given to the subject as well. An example of the drug card is provided in Appendix 19.1. As shown in Table 6, an extra bottle (#14) will be dispensed at Week 2 to the subject to hold at home until the end of the study in case of shortage due to scheduling conflicts or other unanticipated circumstances. Drug accountability and compliance will be performed by the clinical site at each clinic visit. The subject will be instructed to return all study bottles, including bottle #14 at the last clinic visit.

The subject will be asked to bring all bottles and the drug cards at each subsequent visit for accountability. Bottle #14 will be re-dispensed after performing accountability. The first time that investigational products are dispensed, the subject will also be given a copy of the Medication Guide for HORIZANT Extended-Release Tablets (Appendix 19.2).

Table 6: Schedule for Dispensing Study Drug Bottles

Study Visit	Study Week	Bottle #s Dispensed	# Tablets ^a	Anticipated Usage	Anticipated Return	Return for Accountability
1	Day -1 ^b	Dispense #1	30	12	18	
2	2	Dispense #2 & #14	30	28	2	Bottle #1
3	4	Dispense #3 & #14	30	28	2	Bottle #2 & #14
4	6	Dispense #4 & #14	30	28	2	Bottle #3 & #14
5	8	Dispense #5 & #14	30	28	2	Bottle #4 & #14
6	10	Dispense #6 & #14	30	28	2	Bottle #5 & #14
7	12	Dispense #7, #8, & #14	60	56	4	Bottle #6 & #14
8	16	Dispense #9, #10 & #14	60	56	4	Bottle #7, #8, & #14
9	20	Dispense #11, #12 & #14	60	56	4	Bottle #9, #10 & #14
10	24	Dispense #13 & #14	30	28	2	Bottle #11, #12 & #14
11	26	Dispense #14	30	6	24	Bottle #13 & #14
12	27	none				Bottle #14
T	otal:		420	354	66	

^a Does not include Bottle #14 tablets until Week 26.

